Level of Function 1	Bed Activity
Level of Function 2	Able to Sit
Level of Function 3	Able to Stand
Level of Function 4	Walks < 20 feet
Level of Function 5	Walks > 50 feet

The current mobility practices and LOF assessment for patients admitted to the CICU of the Jewish General Hospital were reviewed by a nurse educator on two separate dates as part of continuous quality improvement requested by the quality of care committee of the division of cardiology. We looked at a convenience sample of patients in the CICU on two separate dates. There were 26 patients in the analysis (mean age 71.7 years old, standard deviation (SD) ± 10.9 , female 38.4% (n=10)). There were 10 patients (38.5%) who would not be initially eligible for entry into the study (see eligibility criteria below; four due to age, two on noninvasive or invasive ventilation, two with a transvenous pacemakers, and two who were not hemodynamically stable). For patients who were initially eligible for the study, the mean prehospital LOF was 4.7 (SD ± 0.6) and the mean LOF on CICU admission was 2.3 (SD ± 1.2). Of the eligible patients, 14 patients (87.5%) said they would agree to participate in an EM study and 12 patients (75%) were followed prior to hospitalization by a hospital-affiliated cardiologist.

VI. METHODS

Design, participants and setting

An EM program is being developed as a quality improvement project in conjunction with the Quality and Safety Committee of the Division of Cardiology at the Jewish General Hospital (JGH). For our study, we will perform a prospective, pre/post-EM intervention study in adults aged ≥ 60 years old admitted to the CICU at the JGH. During a 3-month period, we will prospectively enrol patients to the pre-intervention cohort. The EM intervention will then be implemented. During a 12-month period, we will prospectively enrol patients to the intervention cohort. 1 and 12 months following hospital discharge, patients in the pre-intervention and post-intervention cohorts will be contacted by phone by a member of the research team to assess for functional status and quality of life measures.

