Prior to the implementation of the EM intervention, nurses will ascertain and record the prehospital LOF, admission LOF, and LOF on the day of CICU transfer (Appendix A), but will continue usual mobilization practices. Patients who meet eligibility criteria for the EM intervention will be prospectively enrolled over a 3-month period (“pre-intervention cohort”) by a member of the research team during CICU admission. Informed consent will be obtained by a member of the research team. Following discharge, a member of the research team will review the medical record to extract demographic data (age, sex), comorbid illnesses, primary admission diagnosis, frailty status, adverse events during mobilization (falls, dislodgements, and injuries), mobilization activities, length of critical care unit stay, length of hospital stay, mortality, and discharge location.

Intervention

On admission to the CICU, the patient’s treating nurse will assess the patient for the EM program. Patients participating in the EM program will be assessed for enrolment in our study by a member of the research team and will obtain informed consent during CICU admission (“intervention cohort”). The potential participants are likely to be competent and medically fit to be approached for informed consent as patients who are not medically fit will be excluded from the early mobilization program based on clinical factors, which include hemodynamic criteria.

The EM program consists of a progression of functional activities from LOF 0 (lowest mobility) to 5 (highest mobility). Each LOF has 3 primary activities designed to promote the patient to the next level. The nurse will begin with mobility activities based on the LOF that matches the patient’s current status. The nurse and clinical partner will attempt and/or complete each LOF activity once per shift. Physiotherapy assistance is available if required, although not obligatory. Nurses will also provide documentation and education to patients and families on

how to perform and assist with certain activities. LOF, activity attempts/completion, and adverse safety events will be recorded on an EM flowsheet. The intervention will start while the patient is in the CICU and will continue until discharge from the CICU.

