In the patients wearing the accelerometer, data will be recorded on the total time spent in each mobility position, the daily average time spent in each mobility position, the average duration of time for each bout of sitting, standing, and walking, and sleep duration. The step count will also be recorded. The change in skeletal muscle mass from CICU admission to hospital discharge will be recorded.

We will determine which covariates predict improvement in LOF (“responsiveness”) and which ones do not (“non-responsiveness”). We will assess the recovery of physical function at 1 month and 12 months as measured by the SF-36 physical component summary score. We will compare the SF-36 scores of the highest scoring tertile of LOF on hospital discharge with the lowest scoring tertile. We will also compare hospital readmission at 30 days and discharge home vs. healthcare facility.

For safety, we will record the composite and individual components of the number of falls, injuries, and dislodgements over the total number of attempted mobility activities. The results from the intervention cohort will be compared to the pre-intervention cohort for all results.

Data Collection Procedures

Following discharge, a member of the research team will capture the following hospitalization data from the electronic medical record (Chartmaxx, Quest Diagnostics, Madison, New Jersey) for each subject: age, sex, primary admission diagnosis, comorbidities, level of function assessments, CFS score, length of CICU stay, length of hospital stay, discharge location, and referral to cardiac rehabilitation.

Availability of Participants

In the fiscal year 2016-2017, there were 1,356 admissions to the JGH CICU (mean age 68 years old; 477 female (35%)). There were 1,034 patients (76.3%) age ≥ 60 years old. The mean CICU length of stay was 3.3 days and the mean hospital length of stay was 9.5 days. Only one in five patient stays was less than 24 hours in length.

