From the pilot data, we conservatively estimate that about one-third of patients will not be eligible for the study and about 70% will agree to participate. We estimate that the loss of patients to 12 month follow-up will be approximately 10% as the vast majority of CICU patients are followed by hospital-affiliated cardiologists prior to admission or are assigned to one following CICU discharge. Given these estimates, approximately 75 patients are expected to be enrolled and followed during the pre-intervention period and 300 patients are expected to be enrolled and followed during the 12 month intervention period.

Data Analysis

Since the response variable, LOF mobility, is an ordinal variable measured at different timepoints, a cumulative logit model for repeated measurements will be fitted using generalized estimating equations. The model permits us to take into consideration the structure of the correlation between the observations. The model will then be adjusted using covariates of interest, such as age, sex, EM adherence, time spent lying in bed, and illness severity score. Predictors of change in LOF during CICU stay and following hospitalization will be assessed using linear regression. Predictors of EM adherence will also be evaluated using linear regression. All statistical analyses will be performed using SAS version 9.4 by [name], a senior biostatistician affiliated with the Lady Davis Institute Center for Epidemiology.

VII. RESOURCE AVAILABILITY AND SUPPORT

The CICU at the JGH has 16 beds equipped for advanced hemodynamic support and 32 ward beds with telemetry available. Patients are admitted to the CICU mainly for acute primary cardiovascular disease.

The nurse champion's role is to attend EM team meetings, provide education to nursing and clinical partners, and ensure nursing adherence to the protocol. A review of the CICU environment conducted with physiotherapists from the EM team has ensured that the CICU is already equipped with the standard equipment necessary for patient mobilization, particularly for bedbound and immobile patients, and nurses have been trained to use the equipment.

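### The LOF model names an illness severity score that no described data source collects, so the pre/post comparison, as written, has baseline adjustment for age and sex only

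*Combined protocol and SAP*

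**What the plan says.** The study is a "prospective, pre/post-EM intervention study in adults aged ≥ 60 years old", with a 3-month pre-intervention cohort followed by a 12-month intervention cohort (VI. Methods, Design, participants and setting).

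For the primary outcome, LOF, the Data Analysis section states that "a cumulative logit model for repeated measurements will be fitted using generalized estimating equations". It continues: "The model will then be adjusted using covariates of interest, such as age, sex, EM adherence, time spent lying in bed, and illness severity score".

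Two places list what is taken from the chart after discharge:

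- Pre-intervention: "demographic data (age, sex), comorbid illnesses, primary admission diagnosis, frailty status, adverse events during mobilization", followed by "mobilization activities, length of critical care unit stay, length of hospital stay, mortality, and discharge location".
- Data Collection Procedures, for each subject: "age, sex, primary admission diagnosis, comorbidities, level of function assessments, CFS score, length of CICU stay", then hospital stay, discharge location and cardiac rehabilitation referral.

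The severity score is mentioned only in Data Analysis, at the end of the covariate list ("time spent lying in bed, and illness severity score"), with no instrument, scoring rule or time window.

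**The concern.** The two cohorts come from different calendar periods and are not randomised, so the EM effect on LOF is credible only to the extent that the patients are comparable or their differences are adjusted for. How ill a patient is on arrival plausibly affects LOF at CICU discharge and may differ between periods. Severity is the only named baseline covariate besides age and sex. If it is not collected, the comparison is left with those two. If it is built later without a rule, both the instrument and the time window could be chosen after the data have been seen.

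**Working it through.** The plan gives no figure to reproduce on this point. The check sets each covariate named in Data Analysis against the two extraction lists and the other described sources.

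| Covariate named | Pre-intervention list | List for each subject | Other source | Baseline variable? |
|---|---|---|---|---|
| Age | yes | yes | – | yes |
| Sex | yes | yes | – | yes |
| EM adherence | no | no | weekly audits and EM flowsheet, intervention period | no, arises after admission |
| Time lying in bed | no | no | accelerometer substudy only | no, arises after admission |
| Illness severity score | no | no | none described | yes, if taken at admission |

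**Other sources searched for severity.** The EM flowsheet records LOF, activity attempts and completion, and safety events. The CFS measures frailty and is not presented as a severity score. The accelerometer records position and activity, and the bioimpedance scale records body composition. The follow-up calls record LOF, SF-36 and Barthel index. None supplies a severity score or the vital signs and laboratory values to compute one.

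**The two post-admission covariates.** Time lying in bed is available only for participants who accept the substudy, with five monitors and so at most five wearers at a time (Instruments). EM adherence has no counterpart before the program exists. Neither can correct for differences between the cohorts on arrival.

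**What is left.** Five covariates are named. Removing the two that arise after admission leaves three, and removing the one with no source leaves two: age and sex.

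**What is recorded but not named.** Frailty is in both lists, as frailty status in one and as the CFS score in the other. Prehospital LOF is recorded by nurses in the pre-intervention period. It decides eligibility for everyone, because prehospital LOF 0 to 2 is excluded, and LOF assessments are extracted for each subject. Diagnosis and comorbidities are in both lists. Data Analysis names none of these.

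**Can the bias be sized?** Only by assumption. On a mean-difference scale, the shift from an unadjusted covariate is roughly |r| × d × SD. Here r is the correlation of severity with LOF at CICU discharge, d is the difference between cohorts in severity SDs, and SD is that of LOF.

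- The documents give neither r nor d.
- The only local SD for LOF during the CICU stay is 1.2, for LOF on CICU admission (V. Preliminary Studies), among 26 − 10 = 16 initially eligible patients. Using it for discharge LOF is a further assumption.
- With r = −0.2 and d = 0.1: 0.2 × 0.1 × 1.2 = 0.024 level.
- With r = −0.4 and d = 0.2: 0.4 × 0.2 × 1.2 = 0.096 level.
- With r = −0.4 and d = 0.3: 0.4 × 0.3 × 1.2 = 0.144 level.

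The result varies sixfold (0.144 / 0.024) with inputs that nothing in the documents favours. It is also on a different scale from the planned cumulative logit model. It shows only that the size is undetermined.

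**The case against.** Four arguments on the other side have force.

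- **The list is illustrative.** It is introduced as a set of examples, severity comes last, and no item is ranked or given a confounding rationale. A reader might infer that severity is the plan's main control for case mix, or that the adjusted analysis cannot be run without it. The documents support neither reading. The cumulative logit model can be fitted and adjusted for age and sex, and other recorded variables can be added.
- **The extraction lists are not exhaustive.** Readmission at 30 days is a planned comparison yet appears in neither list, and mortality appears only in the pre-intervention one. Absence from the lists may therefore be an omission in drafting. The components might be recoverable from the medical record, but the documents do not say whether they are charted.
- **Eligibility narrows the difference.** Pre-intervention patients must meet the same EM criteria, including the hemodynamic and respiratory exclusions. That plausibly reduces the severity imbalance, but it does not remove differences among patients who pass.
- **Size.** A reader might infer a definite bias, or express one as a share of a detectable difference. The documents state no alpha, power or target effect, so any such share would rest on assumed inputs throughout.

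Taken alone, an undefined score would be close to a missing detail. The point still stands because the comparison is non-randomised, the remaining named baseline adjustment is so thin, and useful baseline variables are already recorded but unused.

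**Conclusion.** The point holds in a limited form. A covariate named for the primary model is undefined and has no described source. Two of the other four named covariates cannot act as baseline adjustment. As written, the cohorts are adjusted at baseline for age and sex only. This weakens confounding control in the pre/post comparison but does not prevent the analysis.

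The conclusion rests on reading the described data sources as they stand, and it would soften if severity components are in fact charted and retrieved. The direction and size of any bias are unknown, and no percentage should be attached to it.

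**What to change.** 1. Name CFS score and prehospital LOF as prespecified covariates in the adjusted cumulative logit model, alongside age and sex. Both are already recorded in both cohorts, so this is a free improvement.
2. Name one illness severity score and add it, or its components, to both extraction lists. Compute it from chart values in the same fixed clock window from CICU admission in both cohorts. A window defined as the time before the first EM activity would not work, because the pre-intervention cohort has no EM activity to mark its end. A short window also limits, without excluding, the use of values recorded after mobilization has begun. This is a cheap improvement: the research assistant already extracts the chart data. The downside is abstraction time and dependence on the components being charted, so their availability should be checked before the score is chosen.

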Yet despite the demonstrated effectiveness and safety in the peer-reviewed literature for EM practices in critical care units, there is evidence that actual practice is lacking.¹⁷ A recent survey of Canadian physicians working in critical care units reported that, while more than half of physicians believed that mobilization should begin as early as possible after unit admission, almost three-quarters felt that they lacked adequate knowledge or training to mobilize patients.¹⁸ In addition, the physicians noted a number of barriers to early mobilization, such as a lack of a standardized protocol and concern over patient safety. Addressing these barriers is essential to the successful implementation of an EM program.

C. Frailty in Older Adults with Cardiovascular Disease

Older adults are at increased risk of developing frailty, a syndrome characterized by sarcopenia, subclinical multi-organ dysfunction, and reduced capability of handling physiological stress.¹⁹ Sarcopenia is the age-related alteration in protein metabolism, decline in muscle mass, strength, and functional capacity. The prevalence of frailty in the critical care unit ranges from 10-40%, depending on the population and setting.^{20, 21} Frail older adults are more likely to have increased muscle loss during periods of acute illness and immobilization, functional decline during hospitalization, and long-term disability following discharge. Frailty in cardiovascular patients is also a strong predictor beyond the chronological age of increased morbidity, hospital and critical care unit stays, mortality, discharge to rehabilitation facilities and institutionalization, and higher rates of readmission. Early progressive mobilization activities may have an even greater impact on frail older adults than on their non-frail counterparts.

D. Knowledge gaps targeted in this proposal

Recent reviews of EM programs in the peer-reviewed literature have identified a number of evidence gaps to be directly addressed by this study.²²

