1. Safety and feasibility of EM in the CICU: The majority of EM intervention studies were performed in the medical intensive care unit or in populations with low rates of primary acute cardiovascular disease and it is unknown whether the findings can be generalized to the CICU. The CICU contains a unique population of patients with primary cardiovascular disease, high illness acuity, and a considerable burden of non-cardiovascular disease.²³ Barriers to mobility for cardiac patients may also differ from those of the general critical care population. To date, minimal data exist in the literature on the use of EM in acute cardiovascular populations.^{5, 24} An expert panel from Health Quality Ontario reviewed the literature for articles assessing EM interventions in hospitalized acute heart failure patients and could not identify any relevant studies.²⁵ A retrospective Canadian study of post-TAVR patients demonstrated a reduction in median hospital length of stay with an early discharge protocol including EM as part of a multimodal intervention strategy.²⁶

2. EM in older adults: Whether older adults, particularly frail older adults, benefit more from EM than younger or nonfrail older adults is uncertain. Prior EM intervention studies were composed of younger patient cohorts and there have been no studies that specifically focus on EM in older adults.²⁴

3. EM and patient-centered outcomes: Prior studies on the impact of EM on outcomes have focused mainly on healthcare resource outcomes (i.e., length of stay, readmission rates) and there are limited data on the effect of EM on patient-centered outcomes. The Canadian Institute for Health Research has identified patient-centered research as a priority for the healthcare system.²⁷ Health-related quality of life and functional status are patient-centered measures that are recommended as key metrics when studying older adults with cardiovascular disease.²⁸

4. Lack of published nurse-driven EM protocols

Prior published EM protocols typically include intensive involvement in daily EM by physiotherapists.^{22, 29} However, given the limited availability of physiotherapists for 24/7 care in the critical care setting and the need for protocol generalizability, it is essential to establish a protocol that can be easily implemented by nursing staff and will provide enough details for replication.

5. Knowledge translation

[figure not shown]

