There are few available tools on how to implement an EM program, particularly in an acute cardiovascular unit. A lack of written protocols or guidelines, as well as insufficient clinician knowledge, has been identified as a barrier to implementing EM in critical care units.¹⁸

6. Patient positioning and activity in patients with acute cardiovascular disease: Precise identification of patient position (lying, sitting, and standing) and physical activity using body-worn sensors is now possible due to improvement in accelerometer technology. Accelerometry has been validated in numerous populations, including in the ICU, mainly in the context of mechanically ventilated patients.³⁰ However, previous studies in the ICU were limited by small sample sizes and short duration of patient monitoring, ranging from 60 minutes to 48 hours, and monitoring did not extend beyond ICU unit stay.³⁰ *There are also no studies in the literature specifically looking at positioning and activity in patients with acute CV disease.* It is important to understand the time spent in the different mobility positions and the relationship with functional outcomes in older adults with acute CV disease. Decreasing the duration of time spent in a lying position is a potentially modifiable factor.

V. PRELIMINARY STUDIES

During my Cardiac Intensive Care fellowship at Cedars-Sinai Medical Center in Los Angeles, CA, I participated in the EM program and instituted frailty screening in the CICU. We used a level of function (LOF) assessment tool in the EM program that ranged from 1 to 5, where 1 was bedbound and 5 was ability to walk > 50 feet (see sidebar). Preliminary analysis of the retrospective cohort of 264 patients with acute cardiovascular disease undergoing EM showed that 90 (34.1%) patients were frail, 65 (24.6%) were vulnerable, and 109 (41.3%) were not frail. We found a moderate correlation between prehospital LOF and frailty ($r = -0.580, P=0.01$). Prehospital LOF was higher in nonfrail elderly than in frail elderly (mean score of 3.71 ± 0.61 vs. 2.59 ± 1.03 ; $P < 0.001$). LOF improved in both nonfrail and frail elderly during CICU stay, however, there was greater improvement in LOF in the frail group (mean increase of 0.53 vs 0.70; $P < 0.01$). The initial data analysis suggests that frailty status is a potential predictor of responsiveness to EM. Further analysis of this dataset is needed to identify other predictors of responsiveness to EM in the CICU.

Progressive Mobility	

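### The regression of change in LOF, as specified, mixes recovery with response to EM, so its predictors should not be reported as responsiveness to EM

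*Combined protocol and SAP*

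**What the plan says.** - **VI. Methods, Outcome Measures:** "We will determine which covariates predict improvement in LOF". The protocol labels such covariates *responsiveness* and the others *non-responsiveness*.
- **VI. Methods, Data Analysis:** "Predictors of change in LOF during CICU stay and following hospitalization will be assessed using linear regression". Nothing states which cohort or cohorts enter, whether cohort is a term, or whether any interaction is fitted. The cumulative logit GEE model for LOF is described as covariate-adjusted, again with no interaction named.
- **VI. Methods, Outcome Measures:** "The results from the intervention cohort will be compared to the pre-intervention cohort for all results". No model or test is attached to this sentence.
- **V. Preliminary Studies**, on 264 patients who all underwent EM: "The initial data analysis suggests that frailty status is a potential predictor of responsiveness to EM". The basis is that "there was greater improvement in LOF in the frail group (mean increase of 0.53 vs 0.70", with the nonfrail figure first.
- **IV.C:** "Early progressive mobilization activities may have an even greater impact on frail older adults than on their non-frail counterparts".
- **IV.D**, in a list of gaps that the study says it will address directly: "Whether older adults, particularly frail older adults, benefit more from EM than younger or nonfrail older adults is uncertain".

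**The concern.** Whether frail patients gain more from EM than others is a question of effect modification. It needs the EM effect in frail patients set against the EM effect in nonfrail patients, and so it needs the pre-intervention cohort. A regression of change on covariates asks who improved.

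The two questions differ whenever patients can recover without EM. The hospital's own convenience sample leaves room for that: among eligible patients "the mean LOF on CICU admission was 2.3", against a prehospital mean of 4.7. The documents do not say how much of that gap closes under usual care.

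At stake is a published statement about who responds to EM. Followed as written, the plan could report a purely prognostic covariate as a predictor of responsiveness. It could also call a covariate non-responsive when the EM effect does vary with it.

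**Working it through.** The plan gives no figure for this analysis (no alpha, power or effect size), so there is nothing to reproduce.

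**Inputs from the documents**
- Expected patients: 75 pre-intervention and 300 intervention (Availability of Participants), taken as stated.
- Frailty share: 34.1%, i.e. 90 of 264, with 109 not frail and 65 vulnerable (V. Preliminary Studies).
- Difference in LOF gain, frail minus nonfrail: 0.70 − 0.53 = 0.17, reported with P < 0.01. It comes from another hospital's 1-5 scale; this study uses a newly developed 0-5 tool.

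**Assumptions:** binary frailty, equal frailty share in both cohorts, two-sided 5% test, and an SD of change that the documents do not give.

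**Step 1. What the coefficient estimates.** Let r be the frail-minus-nonfrail difference in recovery without EM, and m the difference in EM effect.
- Pre-intervention cohort: r. Intervention cohort: r + m.
- Least squares with a cohort main effect weights the two by n·p·(1−p). With equal p the weights are 75/375 = 0.2 and 300/375 = 0.8.
- Result: 0.2r + 0.8(r + m) = r + 0.8m.

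**Step 2. The preliminary 0.17.** All those patients had EM, so 0.17 = r + m. It fits equally well:
- r = 0.17, m = 0 (recovery only);
- r = 0, m = 0.17 (response only);
- r = 0.34, m = −0.17 (frail patients benefit less).

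Conversely, r = 0.17 with m = −0.17 gives a coefficient of 0 in the intervention cohort, so a real modifier would usually be called non-responsive.

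**Step 3. A range for the SD of change.** If the preliminary P < 0.01 came from a t-test (not stated), the SD can be at most 0.17 / (t × √(1/n₁ + 1/n₂)):
- 90 vs 109: 0.17 / (2.601 × 0.1424) = 0.46.
- 90 vs all 174 others: 0.17 / (2.595 × 0.1298) = 0.50.

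Because scale and setting differ here, 0.8-1.2 is carried as a second, assumed range.

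**Step 4. Standard errors**
- Frailty coefficient, intervention cohort: SD × √(1/102.3 + 1/197.7) = 0.1218 × SD.
- Cohort-by-frailty interaction: SD × √(1/25.6 + 1/49.4 + 1/102.3 + 1/197.7) = 0.2723 × SD, which is √5 = 2.24 times larger.

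Power = Φ(δ/SE − 1.96) + Φ(−δ/SE − 1.96). Detectable interaction at 80% power = 2.802 × SE. CI half-width = 1.96 × SE.

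| SD of change | Frailty flagged when r = 0.17, m = 0 (n = 300) | Detectable interaction (levels) | 95% CI half-width | Power for m = 0.17 |
|---|---|---|---|---|
| 0.46 | 86% | 0.35 | 0.25 | 27% |
| 0.50 | 80% | 0.38 | 0.27 | 24% |
| 0.8 | 41% | 0.61 | 0.43 | 12% |
| 1.2 | 21% | 0.92 | 0.64 | 8% |

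The second column is power to find an assumed real difference in recovery, not an error rate. It shows how often such a difference would be labelled responsiveness when EM works equally in both groups.

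**The case against.** **The label is defined on the spot.** Outcome Measures defines *responsiveness* as predicting improvement, and the Data Analysis sentence speaks only of change in LOF. That is fair, and it makes the remedy small. But Preliminary Studies uses the same word for response to EM, and IV.D promises to address differential benefit, so readers will take it in that sense.

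**The between-cohort comparison may cover predictors.** The sentence on comparing all results could be meant that way. A reader might infer that the plan rules out an interaction; it does not, it leaves one unspecified. Even so, separate regressions in each cohort, without a test of the difference, would not answer the question.

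**The regression still carries information on response.** A reader might infer that it captures recovery and nothing of response. Step 1 shows otherwise: m is in the coefficient, but cannot be separated from r.

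**The right test is weak.** This stands. The interaction has low precision and is still exposed to secular change between the two periods. That argues for calling it exploratory and reporting an interval. It does not make the present label valid.

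**The analysis is peripheral.** This also stands. It is in neither hypothesis and none of the five aims, and is not a listed primary or secondary outcome.

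**Conclusion.** The concern holds as a matter of labelling and a missing specification. The stated regression yields r + m or r + 0.8m and never m alone; the factor 0.8 assumes equal frailty shares. This is algebra and does not depend on the SD. How often a prognostic difference of 0.17 would be mislabelled does depend on it: 80%-86% at SD 0.46-0.50 and 21%-41% at SD 0.8-1.2. The lower SD range rests on a t-test having been used, the higher is assumed, and the 0.17 is borrowed from a different scale and hospital.

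Two further inferences are not supported. The preliminary frailty finding is not shown to be wrong, since the data fit a true differential response as well as none. Nor do the documents settle the size or direction of any distortion from leaving baseline LOF out of this regression.

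Severity is minor to should-fix: non-primary, outside the aims, and with no bearing on the main comparison of cohorts.

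**What to change.** 1. Report the linear-regression results as predictors of recovery (change in LOF), and drop *responsiveness* for them.
2. For response to EM, prespecify one interaction, cohort by Clinical Frailty Scale score, fitted in both cohorts together and adjusted for admission and prehospital LOF. Report it with a 95% CI and label it exploratory.
3. The planned cumulative logit GEE is a natural place for it, because it is already the plan's model for LOF. This is not a claim that it beats a linear model of change: neither scale is free of floor and ceiling artefact, and the report should say so.
4. Do not use EM adherence as the modifier, because the pre-intervention cohort has no EM programme to adhere to.

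**Cost.** Analysis wording only. Prehospital LOF is needed for eligibility; prehospital, admission and transfer LOF are recorded in the pre-intervention cohort; LOF assessments and frailty score are extracted for every subject. The price is an imprecise answer: the report must state that a null interaction does not exclude differential benefit, and that a difference between periods could have other causes.
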